## 2.3 Exploratory Objectives

To evaluate the effect of TAS-205 on the urinary excretion of tetranor-PGDM and tetranor-PGEM in pooled urine samples after twice-daily oral administration for 24 consecutive weeks, as well as the relationship between the urinary excretions and efficacy of TAS-205 in patients with DMD, and also to evaluate the change in the urinary excretion of creatinine and creatine in pooled urine samples after twice-daily oral administration of TAS-205 for 24 consecutive weeks in patients with DMD in an exploratory manner.

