# 3. Study Design

This study is a double-blind, randomized study to evaluate the efficacy of TAS-205 for deterioration of physical function (e.g., motor function, muscle volume, muscle strength) compared with placebo in patients with DMD; that is, the study is designed as an exploratory efficacy study.

The target total sample size of 33 patients will be obtained through central registration.

Subjects will be enrolled and randomized to low-dose group (6.67 to 13.33 mg/kg/dose), high-dose group (13.33 to 26.67 mg/kg/dose), or placebo group (randomization ratio: 1:1:1), and receive the investigational product orally twice daily, once after breakfast and once after dinner, for 24 consecutive weeks starting after dinner on Day 1 (subjects will be hospitalized on Day -2 within 12 days after enrollment and start Day 1 within 14 days after enrollment) to evaluate the efficacy in a double-blind manner. Subjects will receive the number of tablets per dose specified based on their body weights measured within 14 days before enrollment, as shown in Table 7.1.1-1.

The study design is shown in Figure 3-1 below.

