## 2. Target Sample Size and Rationale for the Sample Size

Target sample size: a total of 33 subjects (11 subjects for each group)

Given that DMD is a rare disease that allows only limited recruitment of subjects and that this study is primarily intended to evaluate the efficacy of TAS-205 in an exploratory manner, the sample size was determined not statistically, but based on feasibility.

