## **6.6** Exploratory Analysis

The following analyses will be performed in the PPS. The analysis of %MVI of muscle volume measurement (skeletal muscle CT) will be performed in the lower leg, thigh, and thigh + lower leg.

- (1) 6MWD
  - For the group combining all groups, the correlation coefficients (Pearson and Spearman) of 6MWD at Week 24 and %MVI (%) of muscle volume measurement (skeletal muscle CT) will be calculated.
  - For each group and the group combining all groups, the correlation coefficients (Pearson and Spearman) of the changes in 6MWD at Week 24 and the changes in MVI (%) of the muscle volume measurement (skeletal muscle CT) in both legs and P values for the correlation coefficients will be calculated. In addition, subgroup analysis will be conducted for the following items.
    - Subgroup analysis: Baseline 6MWD ( $\leq$ 350 m, and  $\geq$ 350 m)
  - Analysis of covariance will be performed using the following variables as conditions.
     Objective variable: Change in 6MWD at Week 24
     Explanatory variables: Baseline 6MWD, age, presence or absence of the history of steroid use, baseline %MVI (%) in both legs, and changes in %MVI (%) in both legs at Week 24
     In addition, subgroup analysis will be conducted for the following items.
     Subgroup analysis: Baseline 6MWD (<350 m, and ≥350 m)

  - For each group and the group combining all groups, the correlation coefficients (Pearson and Spearman) of the changes in 6MWD at Week 24 and the change rates of urinary tetranor-PGDM/creatinine concentration ratio and urinary tetranor-PGDM on Day 168 and P values for the correlation coefficients will be calculated. In addition, subgroup analysis will be conducted for the following items.

Subgroup analysis: Baseline 6MWD (<350 m, and  $\geq 350 \text{ m}$ )

- Analysis of covariance will be performed using the following variables as conditions.

Objective variable: Change in 6MWD at Week 24

Explanatory variable: Baseline 6MWD, age, presence or absence of the history of steroid use, baseline urinary tetranor-PGDM/creatinine concentration ratio, and the change rate of urinary tetranor-PGDM/creatinine concentration pay 168

In addition, subgroup analysis will be conducted for the following items.

Subgroup analysis: Baseline 6MWD (<350 m, and  $\geq 350 \text{ m}$ )

- (2) %MVI (%) of muscle volume measurement (skeletal muscle CT)

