  - For each group and the group combining all groups, summary statistics of baseline %MVI (%) in both legs will be calculated.
  - For each group, summary statistics of baseline %MVI (%) will be calculated, and 2-sample t-test between groups will be performed. In addition, subgroup analysis will be conducted for the following items.
    - Subgroup analysis: Baseline 6MWD (<350 m, and ≥350 m)
  - For the group combining all groups, the correlation coefficients (Pearson and Spearman) of each %MVI (%) at baseline will be calculated.
  - For each group and the group combining all groups, the correlation coefficients (Pearson and Spearman) of the changes in the %MVI (%) in both legs at Week 24 and the change rates of urinary tetranor-PGDM/creatinine concentration ratio and urinary tetranor-PGDM on Day 168, and P values for the correlation coefficients will be calculated. In addition, subgroup analysis will be conducted for the following items.

Subgroup analysis: Baseline 6MWD ( $\leq$ 350 m, and  $\geq$ 350 m)

Analysis of covariance will be performed using the following variables as conditions.
 Objective variables: Changes in %MVI (%) in both legs at Week 24
 Explanatory variables: Baseline %MVI (%) in both legs, age, presence or absence of the history of steroid use, baseline urinary tetranor-PGDM/creatinine concentration ratio, and the change rate of urinary tetranor-PGDM/creatinine concentration ratio on Day 168
 In addition, subgroup analysis will be conducted for the following items.

Subgroup analysis: Baseline 6MWD (<350 m, and ≥350 m)

- (3) Pharmacodynamic Endpoints
  - For each group and the group combining the low-dose group and the high-dose group, summary statistics of the change rates of urinary tetranor-PGDM excretion, urinary tetranor-PGEM excretion, urinary tetranor-PGDM/creatinine concentration ratio, and urinary tetranor-PGEM/creatinine concentration ratio will be calculated at each time point, and 1-sample t-test using the change rate = 0% as null hypothesis will be conducted at each time point. In addition, subgroup analysis will be conducted for the following items.

Subgroup analysis: Baseline 6MWD (<350 m, and ≥350 m)

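### The two PGDM models in SAP 6.6 pool the arms without an assigned-group term, so their slope mixes the arm contrast with any within-arm link; report them with and without that term

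*SAP*

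**What the plan says.** Protocol 2.3 sets as an exploratory objective to evaluate "the relationship between the urinary excretions and efficacy of TAS-205". SAP 6.6 serves it with correlations and analyses of covariance, introduced by "The following analyses will be performed in the PPS".

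- **6MWD on PGDM:** "Explanatory variable: Baseline 6MWD, age, presence or absence of the history of steroid use, baseline urinary tetranor-PGDM/creatinine concentration ratio", and then the PGDM/creatinine change rate on Day 168.
- **%MVI on PGDM:** "Explanatory variables: Baseline %MVI (%) in both legs, age, presence or absence of the history of steroid use, baseline urinary tetranor-PGDM/creatinine concentration ratio", and then the same change rate.
- **6MWD on %MVI:** "Explanatory variables: Baseline 6MWD, age, presence or absence of the history of steroid use, baseline %MVI (%) in both legs", and then the Week 24 change in %MVI.

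Assigned group is in none of the three lists, although every MMRM in SAP 6.1, 6.2.1 and 6.3 names it as a covariate. The covariance bullets do not say whether they run per arm or over all arms. They are repeated by baseline 6MWD below or at least 350 m.

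The companion PGDM correlations in SAP 6.6 are planned, with P values, for each arm and for all arms together. Protocol 13.1.3.4 planned such correlations within each treatment group only. The trial aims for 33 subjects, 11 per arm, and "the sample size was determined not statistically, but based on feasibility".

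**The concern.** Protocol 1.4.2.2 reports that the Phase I study in DMD suggested a fall in urinary PGDM with increasing dose. The marker may therefore act partly as a proxy for the randomised arm. A model that pools the arms without an arm term estimates one slope from two sources: how arm means of outcome move with arm means of PGDM, and how boys within an arm differ. The first is the treatment comparison that the t-tests and MMRM already make. Only the second is new information on a within-arm link.

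Two misreadings are possible. An arm difference arising through another pathway could be presented as a PGDM-efficacy relationship within patients. A real within-arm relationship could be missed because the arm means do not follow it. Protocol 14.1 and 14.2 intend efficacy to be judged from numerical trends across endpoints, with a 48-week confirmatory study to follow. A pooled marker result could carry weight there as mechanistic support.

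**Working it through.** The plan states no power, alpha or error rate for SAP 6.6, so there is no figure to reproduce. The only design figure, 3 × 11 = 33, is consistent.

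**Inputs.** From the documents: 33 subjects, 1:1:1 allocation, and the listed model terms. Assumed: two-sided 0.05 (SAP 8.3 gives a two-sided 95% level for the MMRM only), within-arm SD of 1 for marker and outcome, and a low-dose effect half the high-dose effect. The sizes of the shifts are also assumed.

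**1. Pooling.** The model has 6 parameters: an intercept, four baseline covariates and the change rate. Per arm, 11 − 6 = 5 residual df. An arm split by baseline 6MWD has about 5 or 6 subjects, which leaves none. Pooled, 33 − 6 = 27, or 33 − 8 = 25 with two arm indicators.

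**2. What the pooled slope estimates.** Let the marker's arm means be 0, d/2 and d. The between-arm variance is d²/6, and the within-arm variance is 1. Ignoring the baseline covariates,

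pooled slope = (within slope + (d²/6) × between slope) / (1 + d²/6).

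The between-arm weight is 0.167/1.167 = 14% at d = 1, 0.667/1.667 = 40% at d = 2 and 1.5/2.5 = 60% at d = 3. At d = 2 the pooled slope is 0.6 × within + 0.4 × between.

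**3. No within-arm slope.** Rejection rates for the PGDM term, 4,000 simulated trials per row:

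| High-dose outcome effect (SD) | PGDM shift (SD) | Without arm | With arm |
|---|---|---|---|
| 0.5 | 1 | 6.4% | 4.8% |
| 0.5 | 2 | 9.5% | 4.8% |
| 0.8 | 1 | 10.4% | 5.2% |
| 0.8 | 2 | 17.5% | 5.2% |
| 1.0 | 1 | 11.6% | 5.4% |
| 1.0 | 2 | 23.7% | 5.0% |
| 1.5 | 1 | 18.5% | 5.1% |
| 1.5 | 2 | 43.6% | 4.9% |

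The all-arms Pearson test behaves alike (27.7% at 1.0 and 2 SD). If either true arm effect is zero, the model without arm rejects 4.7% to 5.4%.

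**4. Within-arm correlation −0.5, PGDM shift 2 SD.** A positive outcome effect is a benefit, the direction that the within-arm slope predicts. The between slope is the outcome effect divided by −2.

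| High-dose outcome effect (SD) | Pooled slope | Without arm | With arm |
|---|---|---|---|
| −1.0 | −0.3 + 0.2 = −0.1 | 6.7% | 78.2% |
| −0.5 | −0.3 + 0.1 = −0.2 | 24.4% | 77.8% |
| 0 | −0.3 | 54.3% | 78.1% |
| 0.5 | −0.3 − 0.1 = −0.4 | 81.6% | 78.7% |
| 1.0 | −0.3 − 0.2 = −0.5 | 95.0% | 77.8% |

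The last row is full mediation: slope −0.5 × shift −2 = 1.0. There the pooled model is the more powerful.

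A re-run of selected rows of both tables, with baseline covariates unrelated to marker and outcome, gave rates within 3 percentage points of these.

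**5. Per-arm correlations already planned.** With n = 11, t(0.975, 9) = 2.262, so |r| must exceed 2.262/√(9 + 2.262²) = 0.60 for P < 0.05. Simulated power at r = 0.5 is about 37%, with no covariate adjustment.

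**The case against.** The best defence is that the pooled slope answers a legitimate question. The objective is the relation between urinary excretion and efficacy, and suppression by the drug is part of that relation. The rejections in the first table are not false for the overall marker-outcome association, which exists in those scenarios. They are false only for a within-arm slope. Adjusting for arm removes the randomised part of the signal. What remains is not randomised: Protocol 1.1 links PGDM to age and ambulatory status. This stands, and it rules out treating the arm-adjusted model as the sole valid evidence.

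It is also true that pooling is inferred, that SAP 6.6 asks for P values for the correlations and not for the covariance models, and that per-arm correlations and scatter plots are planned. The section is exploratory and carries no decision rule. These points limit the weight of the concern. They do not answer it, because nothing in the plan separates the two sources in the pooled results and the per-arm correlations are weak.

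A reader might infer more than the documents support:

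- **That chance arm differences inflate the error rate.** They do not. Inflation needs true arm effects on both marker and outcome.
- **That most of the PGDM spread lies between arms.** Protocol 1.4.2.2 gives no size or SD, and its data come from 7 days of repeated dosing. Protocol 1.3.2 says the high dose had not been given before. The between-arm share is 40% at a 2 SD shift and passes half only at larger shifts.
- **That the 6MWD-on-%MVI model is equally affected.** The documents report no drug effect on %MVI, so the case there is weaker.

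**Conclusion.** The point holds for the two PGDM covariance models and for the all-arms PGDM change correlations in SAP 6.6. As written, a small P value cannot be told apart from a repeat of the arm comparison, and a large one does not exclude a within-arm association.

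Over the assumed grid, rejection without a within-arm slope is 6% at the smallest pair of effects and about 10% to 44% at the others, against about 5% with arm included. Dilution in the other direction is 54% against 78% power when the outcome does not differ by arm, and worse when it differs in the opposing direction. When the arm effect agrees with the within-arm slope, there is no loss. All these sizes rest on assumed shifts, since the documents give neither a PGDM SD nor an expected effect.

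The consequence is modest. It concerns how an exploratory result is read, and does not touch the primary endpoint or the treatment comparisons.

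**What to change.** In SAP 6.6:

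1. State that the covariance models pool the three arms.
2. Report each PGDM covariance model twice, without and with assigned group as an explanatory variable.
3. Beside each all-arms PGDM change correlation, report the partial correlation adjusted for assigned group.
4. Label the unadjusted versions as mixing between-arm and within-arm association, and base any claim of a within-arm relationship on the adjusted version. Do not require every PGDM-efficacy conclusion to rest on the adjusted version alone.
5. Optionally, report the same pair of models for 6MWD on %MVI.

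The change needs SAP wording and one extra model term, with no new data. The adjusted model loses 2 residual df: 27 to 25 overall, and about 10 to 8 in each 6MWD subgroup if the 33 split evenly (16 − 6 and 16 − 8). If the effect runs wholly through PGDM, its power is lower (78% against 95% in the last row of the second table), which is why both versions should be shown. Any exclusions from the PPS would reduce the df further.

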## 7. List of Items Analyzed

A list and summary of the items analyzed, including the above-mentioned items of primary analysis and secondary analysis, as well as the standard items of analysis considering ICH-E3 Guideline are shown in Appendix.

## **8.** General Matters in Data Analysis

## **8.1** Statistical Analytical Software

Generation of the figures, tables and tabulated lists planned in this document will be performed using SAS Version 9.4. The format of output of the results will be RTF.

When any statistical analytical software other than those mentioned above or any self-made software is used, it should be clearly stated in the statistical analysis plan.

## **8.2** General Matters related to Format of Figures, Tables and Tabulated Lists

Details about the form of output of individual figures and tables will be stipulated in the report analysis plan.

The paper size will be A4. Portrait will be used as the standard for figures and summary tables, and landscape will be used as the standard for tabulated lists and data lists. However, it will be decided according to the characteristics of individual figures and tables.

The name of the investigational product and the protocol number will be shown at the left top of each page; the date and time of output and page number will be shown at the right top; the output program name will be shown at the left bottom; and the user ID of the person executing the analytical program will be shown at the right bottom.

## **8.3** Common Rules for Data Processing

- O Rules regarding number of days and period
  - 1. The number of days will be calculated by subtracting the day of start from the day of completion and adding 1.
    - (Example)
    - Number of days of administration: if administration is terminated on the day of the start of administration, the administration period will be 1 day.
    - Duration to the onset of adverse events: If any adverse event occurs on the day after the day of the start of administration, the duration to the first occurrence of adverse event will be 2 days.
  - 2. When the number of days is converted to the number of years, number of months, and number of weeks, 1 year will be counted as 365.25 days, 1 month will be counted as 30.4375 days, and 1 week will be counted as 7 days.
- Rules for number of decimal places and rounding
  - 1. Mean values, standard deviations, and median values will be displayed (rounded) to the place (or decimal place) next to the lowest place of source data.
  - 2. Percentage will be displayed to 1 decimal place (example, 12.3%). Values are rounded to 1 decimal place.
  - 3. In calculation of statistic values such as mean values, standard deviations, and median values, rounding is not performed during the process of calculation. Only the final values obtained as a result of calculation will be rounded.
  - 4. P values will be displayed to 3 decimal places (example, 0.001). The values will be rounded to 3 decimal places.

#### Summary statistics

When summary statistics are displayed, the "number of subjects," "median values," "mean values," "standard deviations," "minimum values," and "maximum values" will be displayed as a set unless otherwise there are any particular reasons.

#### O LOCF

If the data at the last time point of observation are missing, the data which are not missing and have been obtained immediately before that time point will be used for interpolation, irrespective of whether or not the data are within the acceptable range.

Confidence interval of incidences

The confidence interval of incidences (or incidence rates) will be obtained by an exact method based on F distribution.

The number of subjects in the analysis set is put as N and the number of subjects exhibiting adverse events is put as X. Thus, the incidence (P) and the upper limit ( $P_U$ ) and lower limit ( $P_L$ ) of the exact 2-sided 100(1- $\alpha$ )% confidence interval of the incidence will be estimated by the following formulas. In the case of 95% confidence interval,  $\alpha$ =0.05.

Adverse events

Adverse events will be coded according to MedDRA/J, and Preferred Terms (PT) will be used for tabulation unless otherwise specified. The version of MedDRA to be used will be the newest version available as of the time of data fixation as a rule, but it will be decided by the MedDRA manager.

#### O MMRM

The confidence coefficient for estimation of confidence interval will be 2-sided 95%. In the analysis of MMRM, SAS MIXED procedure will be used as shown in the following SAS code.

proc mixed data = INDATA;

class	ATRTN † (ref='1'[Placebo]) AVISITN † SUBJID † ;
model	$AVAL^{\dagger} = BASE^{\dagger} ATRTN AVISITN ATRTN*AVISITN / ddfm = KR ;$
lsmeans	ATRTN*AVISITN / diff cl alpha = 0.05 ;
repeated	AVISITN / subject = SUBJID type = $UN^{\#}$ ;
estimate	"Low Dose TAS-205 Saturation - Week 12" ATRTN -2 1 1 ‡
	ATRTN*AVISITN $-2\ 0\ 1\ 0\ 1\ 0$ / cl alpha = 0.05;
estimate	"Low Dose TAS-205 Saturation - Week 24" ATRTN -2 1 1 ‡
	ATRTN*AVISITN $0 - 2 0 1 0 1 / cl alpha = 0.05$ ;
estimate	"Placebo vs High Dose TAS-205 - Week 12" ATRTN -1 0 1 ‡
	ATRTN*AVISITN $-100010$ / cl alpha = 0.05;
estimate	"Placebo vs High Dose TAS-205 - Week 24" ATRTN -1 0 1 ‡
	ATRTN*AVISITN $0 - 1 0 0 0 1 / cl alpha = 0.05$ ;
estimate	"High Dose TAS-205 Saturation - Week 12 " ATRTN -1 -1 2 ‡
	ATRTN*AVISITN $-1 \ 0 \ -1 \ 0 \ 2 \ 0 \ / \ cl \ alpha = 0.05$ ;
estimate	"High Dose TAS-205 Saturation - Week 24 " ATRTN -1 -1 2 ‡
	ATRTN*AVISITN $0 - 1 0 - 1 0 2 / cl alpha = 0.05$ ;

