# 13.1.3.2 Analysis of the Primary Endpoint

The following analyses will be performed for the primary endpoint, defined as the change from baseline in 6MWD at Week 24:

- (1) Primary analysis
  - To evaluate the efficacy of TAS-205 appropriately, summary statistics will be calculated for each treatment group in the PPS.
- (2) Sensitivity analysis for the primary analysis
  - The analysis described in (1) will be performed in the FAS.

(3) Secondary analyses of the primary endpoint

The following analyses will be performed in the PPS and FAS:

- A 2-sample t-test will be performed between each treatment group and placebo group. This analysis will be performed with and without the LOCF imputation.
- The treatment effect will be estimated using the MMRM. The changes from baseline in 6MWD measured at other time points will also be included in this analysis.
- Using the MMRM, the dose relationship will be analyzed with treatment contrasts of (placebo group, low-dose group, high-dose group) = (-2 1 1), (-1 0 1), and (-1 -1 2). The changes from baseline in 6MWD measured at other time points will also be included in this analysis.

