- (2) The following analyses will be performed for each value measured in each motor function test (time to rise from the floor test, Timed 10-m walk/run test, Timed Up & Go test), measurement of muscle volume (skeletal muscle CT, BIA), lean body mass, quantitative muscle strength assessments (hip flexion/extension, knee flexion/extension, ankle extension/flexion), serum CK concentration (only the serum CK concentration during the hospitalization period will be used for the efficacy evaluation), and pulmonary function test (VC, FVC, FEV1.0, FEV1.0%): In the analysis of the muscle volume measurement (skeletal muscle CT) in the PPS, the subjects of the reference values will be excluded. See Table 10.1 Method to Derive %MVI (%) for derivation of %MVI (%) of the muscle volume measurement (skeletal muscle CT). In quantitative muscle strength assessments, the maximum values in the measurement without compensation will be used.
  - Summary statistics will be calculated at each time point for each treatment group.
  - Summary statistics for the change from baseline will be calculated, followed by a 2-sample t-test between each treatment group and placebo group at each time point. The data at Week 24 will be analyzed with and without the LOCF imputation.
  - With respect to the above 2 analyses, subgroup analysis will be conducted for the following items.

Subgroup analysis: Presence or absence of the history of steroid use, age category ( $\geq$ 5 years and <7 years, and  $\geq$ 7 years), and baseline 6MWD (<350 m, and  $\geq$ 350 m)

- The treatment effect will be estimated at each time point using the MMRM. The changes from baseline in the values measured at other time points will also be included in this analysis. Covariates will be the assigned group, baseline value, time point, and the interaction term of the assigned group and time point.
- Using the MMRM, the dose relationship will be analyzed at each time point with treatment contrasts of (placebo group, low-dose group, high-dose group) = (-2 1 1), (-1 0 1), and (-1 -1 2). Covariates will be the assigned group, baseline value, time point, and the interaction term of the assigned group and time point.

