#### run;

- ATRTN: Treatment group (placebo group [reference group], low-dose group, high-dose group)
   AVISITN: Time point (Week 12, Week24)
  - SUBJID: Patient ID

AVAL: Response variable

BASE: Baseline value

- Contrast coefficient (-2 1 1): Paired comparison of low-dose group saturation Contrast coefficient (-1 0 1): Paired comparison of linear trend Contrast coefficient (-1 -1 2): Paired comparison of high-dose group saturation
- # If convergence is not achieved with UN, TOEP will be used. If convergence is not achieved yet, the following will be used in this order:  $AR(1) \rightarrow CS \rightarrow VC$ .

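### The MMRM code in SAP 8.3 writes its dose-relationship weights in placebo, low, high order but declares placebo the reference level; if SAS then lists placebo last, all six ESTIMATE lines report the wrong contrast

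*SAP*

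**What the plan says.** Protocol 13.1.3.2 and SAP 6.1 define the dose-relationship analysis by "treatment contrasts of (placebo group, low-dose group, high-dose group) = (-2 1 1), (-1 0 1), and (-1 -1 2"). SAP 6.2.1 applies the same three contrasts to the other efficacy endpoints ("Using the MMRM, the dose relationship will be analyzed at each time point with treatment contrasts of" the same three groups), and SAP 6.3 applies them to the pharmacodynamic and exploratory endpoints.

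SAP 8.3, under MMRM, turns this into code: "SAS MIXED procedure will be used as shown in the following SAS code". The code has six ESTIMATE lines, one for each of the three contrasts at Week 12 and at Week 24. Each line has three weights for `ATRTN` and six for `ATRTN*AVISITN`. The one that matters most here reads "Placebo vs High Dose TAS-205 - Week 24' ATRTN -1 0 1", with interaction weights 0 -1 0 0 0 1.

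The CLASS statement in the same code sets `ref='1'` for `ATRTN`, glossed as placebo. The footnote to the code lists "ATRTN: Treatment group (placebo group [reference group], low-dose group, high-dose group") and explains the middle contrast as "Contrast coefficient (-1 0 1): Paired comparison of linear trend". The LSMEANS line requests "ATRTN*AVISITN / diff cl alpha = 0.05". SAP 8.1 names the software: outputs "planned in this document will be performed using SAS Version 9.4".

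**The concern.** ESTIMATE weights carry no level names; the first weight goes to the first level in the working order, and so on. The six lines therefore deliver the planned contrasts only if placebo is the first level when the weights are applied. The code also declares placebo the reference level, and the SAP does not say where that puts it in the list. If the declaration moves placebo to the end, the weights written for placebo, low, high fall on low, high, placebo.

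Evaluating dose relationship is part of the secondary objective (Protocol 2.2), and these contrasts are the analysis named for it. A misplaced weight would give an estimate with a plausible confidence interval under a wrong label. Protocol 14.1 intends efficacy to be read from numerical trends, so a contrast with the wrong sign or the wrong arms would mislead exactly that reading. The SAP plans no check of the coefficients.

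**Working it through.** **Inputs.** Contrasts, labels, model terms and `ref='1'`: SAP 8.3. Group order and 11 subjects per group: SAP 6.1 and SAP 2. Visits: Weeks 12 and 24, from the code footnote. The codes low = 2 and high = 3 are inferred from the order of the footnote; only placebo = 1 is given. The level order after `ref=` is not in the documents, so both cases are worked. SAS was not run.

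**Step 1: reproduce the planned contrasts.** With levels in the order placebo (P), low (L), high (H), all six lines return the stated weights: (-2 1 1), (-1 0 1) and (-1 -1 2) at each week.

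**Step 2: the same weights with placebo last (L, H, P).** The first weight now falls on low, the second on high and the third on placebo.

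| Printed weights | Intended weights on (P, L, H) | Weights on (P, L, H), placebo last | Meaning, placebo last |
|---|---|---|---|
| -2 1 1 | (-2, 1, 1) | (1, -2, 1) | P + H - 2L, none of the planned contrasts |
| -1 0 1 | (-1, 0, 1) | (1, -1, 0) | P - L, no weight on the high dose |
| -1 -1 2 | (-1, -1, 2) | (2, -1, -1) | 2P - L - H, low-dose saturation with its sign reversed |

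The interaction weights shift in the same way, so 0 of 6 lines match the plan. Only the two -1 0 1 lines compare a different pair of arms; the other four use all three arms with misplaced weights.

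**Step 3: would estimability reveal it?** The printed model has 1 (intercept) + 1 (baseline) + 3 (group) + 2 (visit) + 6 (interaction) = 13 columns. With 3 × 11 × 2 = 66 rows the design matrix has rank 7. A contrast is estimable if adding its row leaves the rank unchanged. The rank stays at 7 for all six lines under either level order, so estimability gives no warning.

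**Step 4: size, for illustration.** The documents give no means or SD. Assume a true high-minus-placebo difference of +30 m at Week 24 and three dose patterns. Values are in the order low-dose saturation / placebo vs high / high-dose saturation, in metres.

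| Assumed change P / L / H | Placebo first (as planned) | Placebo last |
|---|---|---|
| Graded: -40 / -25 / -10 | 45 / 30 / 45 | 0 / -15 / -45 |
| High dose only: -40 / -40 / -10 | 30 / 30 / 60 | 30 / 0 / -30 |
| Both doses equal: -40 / -10 / -10 | 60 / 30 / 30 | -30 / -30 / -60 |

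For the graded pattern, placebo last: -40 - 2(-25) + (-10) = 0; -40 - (-25) = -15; 2(-40) - (-25) - (-10) = -45.

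**Step 5: chance that the placebo-vs-high line is negative, graded pattern.** This is a simple two-arm normal approximation, not a fitted MMRM: SE = SD × √(2/11), probability = Φ(-mean/SE).

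| Assumed SD (m) | SE (m) | Placebo first, mean +30 | Placebo last, mean -15 |
|---|---|---|---|
| 40 | 17.1 | 0.04 | 0.81 |
| 60 | 25.6 | 0.12 | 0.72 |
| 80 | 34.1 | 0.19 | 0.67 |

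**The case against.** The strongest reply is that the documents agree among themselves. Every statement of the contrasts uses placebo, low, high; the footnote lists the groups in that order; and the labels match. Nothing in the documents says that declaring a reference moves a level to the end. That is a property of the software. This stands, and it is why the finding is conditional. It does not dispose of the point: the SAP names SAS 9.4, the behaviour can be checked in one run, and the SAP neither states the level order nor asks for it to be confirmed.

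The code is also partly a template, with a bracketed gloss and footnote marks inside the statements, so a programmer must edit it before use. True, but both `ref='1'` and the positional weights are clearly meant to be kept.

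The reach is narrower than the list of endpoints suggests. The interaction weights fit exactly two post-baseline visits. By Table 1 of the protocol they suit 6MWD, the three timed tests and muscle strength. Skeletal muscle CT has one post-baseline visit, pooled urine three, pulmonary function four, and BIA and lean body mass seven. Code for those must be rewritten, and whether the mismatch survives depends on code that the SAP does not show. This stands.

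Finally, the trial is exploratory, was not sized statistically, makes no multiplicity adjustment and attaches no decision rule to these contrasts. The same PROC call prints the correct pairwise differences through LSMEANS, so an attentive analyst could see the disagreement. This limits the harm, but the SAP does not require anyone to compare the two. The means and SDs above are assumptions and show only the form the error would take.

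**Conclusion.** The concern holds in its conditional form. As printed, the code does not guarantee the contrasts that the SAP defines. They result if placebo is the first working level. If `ref='1'` places it last, all six ESTIMATE lines are wrong, and in the graded illustration a true +30 m advantage of high dose over placebo appears as -15 m on the line bearing that label.

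The conclusion rests on one assumption to be confirmed in SAS 9.4 (where the reference level is placed) and one inference (low = 2, high = 3). The mapping of weights and the estimability result are exact given the level order; the metre values and probabilities are illustrative.

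Only the dose-relationship ESTIMATE output is at risk. The primary summary statistics, the t-tests including the combined-dose comparisons, and the MMRM pairwise differences from LSMEANS do not depend on the order. The point should be fixed because it touches a stated secondary objective, but it does not threaten the primary result.

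**What to change.** Take one of two routes.

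- **(a)** Delete `ref='1'` and state the codes 1 = placebo, 2 = low, 3 = high in the SAP. No printed statement needs a reference level, since LSMEANS asks for all differences.
- **(b)** Keep `ref='1'` and, once placebo-last is confirmed, rewrite the weights in the order low, high, placebo:

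| Contrast | `ATRTN` | `ATRTN*AVISITN`, Week 12 | `ATRTN*AVISITN`, Week 24 |
|---|---|---|---|
| Low-dose saturation | 1 1 -2 | 1 0 1 0 -2 0 | 0 1 0 1 0 -2 |
| Placebo vs high | 0 1 -1 | 0 0 1 0 -1 0 | 0 0 0 1 0 -1 |
| High-dose saturation | -1 2 -1 | -1 0 2 0 -1 0 | 0 -1 0 2 0 -1 |

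With placebo last, these weights return the planned values in all three illustrative patterns (45/30/45, 30/30/60, 60/30/30).

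Under either route, confirm the working order from the Class Level Information table or the E option of ESTIMATE. Also require the placebo-vs-high estimate to equal the LSMEANS high-minus-placebo difference at the same week, with the direction of subtraction aligned. Apply the same rule wherever the code is adapted for endpoints with other visit schedules.

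The cost is a few lines of SAP code and one programmed check. Data collection, sample size, the primary summaries and the t-tests do not change.
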